**Table 14.2.8.1: Summary of Antiviral Medication Use After Maintenance Dose**

mITT Population

Variable	GEN-003 60 ug/ M2 50 ug N=xx	Placebo N=xx
Statistic		
Antiviral Medication Use After Maintenance Dose		
Yes	n (%)	n (%)
No	n (%)	n (%)

Program:  
Programming Notes:

Date Produced: mm/dd/yy

- Antiviral medications are defined as medications with an ATC2 Class of 'ANTIVIRALS FOR SYSTEMIC USE'
- Number this table 14.2.8.1 and produce a similar table (14.2.8.2) for the PP population

[Sponsor]

Protocol: [Protocol number]

page x of y

**Table 14.3.1.1: Frequency Table of All Adverse Events by SOC, Preferred Term, and Treatment**

Safety Population

	GEN-003 60 ug/ M2 50 ug N=xx	Placebo N=xx
MedDRA SOC Preferred Term		
Total Number (%) of Subjects With AEs	x (x.x)	x (x.x)
SOC1	x (x.x)	x (x.x)
PT1	x (x.x)	x (x.x)
PT2	x (x.x)	x (x.x)
---		
SOC2		
PT1	x (x.x)	x (x.x)
PT2	x (x.x)	x (x.x)
---		
-----		
SOCn		
PT1	x (x.x)	x (x.x)
PT2	x (x.x)	x (x.x)
---		

Note: Adverse event mapping was based on the MedDRA Version xx.x thesaurus.

Note: Subjects who have the same event more than once are counted only once for the Preferred Term. Subjects who have more than one adverse event within a System Organ Class are counted only once in that System Organ Class.

Program:

Date Produced: mm/dd/yy

[Sponsor]

Protocol: [Protocol number]

page x of y

**Table 14.3.1.2: Frequency Table of All Adverse Events by SOC, Preferred Term, Treatment, and Severity**

Safety Population  
Severity: Grade 1 (Mild)

	GEN-003 60 ug/ M2 50 ug N=xx	Placebo N=xx
MedDRA SOC Preferred Term		
Total Number (%) of Subjects With AEs	x (x.x)	x (x.x)
SOC1	x (x.x)	x (x.x)
PT1	x (x.x)	x (x.x)
PT2	x (x.x)	x (x.x)
---		
SOC2		
PT1	x (x.x)	x (x.x)
PT2	x (x.x)	x (x.x)
---		
-----		
SOCn		
PT1	x (x.x)	x (x.x)
PT2	x (x.x)	x (x.x)
---		

Note: Adverse event mapping was based on the MedDRA Version xx.x thesaurus.

Note: Subjects who have the same event more than once are counted only once for the Preferred Term. Subjects who have more than one adverse event within a System Organ Class are counted only once in that System Organ Class.

Program:

Date Produced: mm/dd/yy

Programming Note: Produce a subtable for each level of severity (Grade 1=Mild, Grade 2=Moderate, Grade 3=Severe, Grade 4=Potentially Life-threatening).

[Sponsor]

Protocol: [Protocol number]

page x of y

**Table 14.3.1.3: Frequency Table of All Adverse Events by SOC, Preferred Term, Treatment, and Causality**

	Safety Population	
	Relationship to Investigational Product: Likely	
	GEN-003 60 ug/ M2 50 ug N=xx	Placebo N=xx
MedDRA SOC Preferred Term		
Total Number (%) of Subjects With AEs	x (x.x)	x (x.x)
SOC1	x (x.x)	x (x.x)
PT1	x (x.x)	x (x.x)
PT2	x (x.x)	x (x.x)
---		
SOC2		
PT1	x (x.x)	x (x.x)
PT2	x (x.x)	x (x.x)
---		
-----		
SOCn		
PT1	x (x.x)	x (x.x)
PT2	x (x.x)	x (x.x)
---		

Note: Adverse event mapping was based on the MedDRA Version xx.x thesaurus.

Note: Subjects who have the same event more than once are counted only once for the Preferred Term. Subjects who have more than one adverse event within a System Organ Class are counted only once in that System Organ Class.

Program:

Date Produced: mm/dd/yy

Programming Note: Produce a subtable for each level of causality/relationship to vaccine (Likely, Unlikely).

**Table 14.3.1.4: Frequency Table of All Adverse Events Leading to Discontinuation of Dosing by SOC, Preferred Term and Treatment**

	Safety Population	
	GEN-003 60 ug/ M2 50 ug N=xx	Placebo N=xx
MedDRA SOC Preferred Term		
Total Number (%) of Subjects With AEs	x (x.x)	x (x.x)
SOC1	x (x.x)	x (x.x)
PT1	x (x.x)	x (x.x)
PT2	x (x.x)	x (x.x)
---		
SOC2		
PT1	x (x.x)	x (x.x)
PT2	x (x.x)	x (x.x)
---		
-----		
SOCn		
PT1	x (x.x)	x (x.x)
PT2	x (x.x)	x (x.x)
---		

Note: Adverse event mapping was based on the MedDRA Version xx.x thesaurus.

Note: Subjects who have the same event more than once are counted only once for the Preferred Term. Subjects who have more than one adverse event within a System Organ Class are counted only once in that System Organ Class.

Program:

Date Produced: mm/dd/yy

[Sponsor]

Protocol: [Protocol number]

page x of y

**Table 14.3.1.5: Frequency Table of Subjects with Adverse Events of Special Interest by SOC, Preferred Term and Treatment**

Safety Population		
	GEN-003 60 ug/ M2 50 ug N=xx	Placebo N=xx
MedDRA SOC Preferred Term		
Total Number (%) of Subjects With an Adverse Event of Special Interest	x (x.x)	x (x.x)
SOC1	x (x.x)	x (x.x)
PT1	x (x.x)	x (x.x)
PT2	x (x.x)	x (x.x)
---		
SOC2		
PT1	x (x.x)	x (x.x)
PT2	x (x.x)	x (x.x)
---		
-----		
SOCn		
PT1	x (x.x)	x (x.x)
PT2	x (x.x)	x (x.x)
---		

Note: Adverse event mapping was based on the MedDRA Version xx.x thesaurus.

Note: Subjects who have the same event of Special Interest more than once are counted only once for the Preferred Term. Subjects who have more than one adverse event of Special Interest within a System Organ Class are counted only once in that System Organ Class.

Program:

Date Produced: mm/dd/yy

[Sponsor]

Protocol: [Protocol number]

page x of y

**Table 14.3.1.6: Frequency Table of All Adverse Events with ≥ 5% Occurrence by SOC, Preferred Term, and Treatment**

Safety Population

	GEN-003 60 ug/ M2 50 ug N=xx	Placebo N=xx
MedDRA SOC Preferred Term		
Total Number (%) of Subjects With AEs	x (x.x)	x (x.x)
SOC1	x (x.x)	x (x.x)
PT1	x (x.x)	x (x.x)
PT2	x (x.x)	x (x.x)
---		
SOC2		
PT1	x (x.x)	x (x.x)
PT2	x (x.x)	x (x.x)
---		
-----		
SOCn		
PT1	x (x.x)	x (x.x)
PT2	x (x.x)	x (x.x)
---		

Note: Adverse event mapping was based on the MedDRA Version xx.x thesaurus.

Note: Subjects who have the same event more than once are counted only once for the Preferred Term. Subjects who have more than one adverse event within a System Organ Class are counted only once in that System Organ Class.

Program:

Date Produced: mm/dd/yy

Programming Notes:

- Include all SOC/PT where the active treatment group has a ≥ 5% occurrence rate for that SOC/PT.

[Sponsor]

Protocol: [Protocol number]

page x of y

**Table 14.3.1.7: Summary of Local Reactions and Systemic Events Occurring Within 7 Days Postdose by Treatment and Maximum Severity**  
Safety Population

Local Reactions and Systemic Events	Grade [1]	GEN-003 60 ug/ M2 50 ug N=xx	Placebo N=xx
Any Local Reaction or Systemic Event	Any	n (x.x%)	n (x.x%)
	1	n (x.x%)	n (x.x%)
	2	n (x.x%)	n (x.x%)
	3	n (x.x%)	n (x.x%)
	4	n (x.x%)	n (x.x%)
Any Local Reaction	Any	n (x.x%)	n (x.x%)
	1	n (x.x%)	n (x.x%)
	2	n (x.x%)	n (x.x%)
	3	n (x.x%)	n (x.x%)
	4	n (x.x%)	n (x.x%)
Pain	Any	n (x.x%)	n (x.x%)
	1	n (x.x%)	n (x.x%)
	2	n (x.x%)	n (x.x%)
	3	n (x.x%)	n (x.x%)
	4	n (x.x%)	n (x.x%)
Tenderness	Any	n (x.x%)	n (x.x%)
	1	n (x.x%)	n (x.x%)
	2	n (x.x%)	n (x.x%)
	3	n (x.x%)	n (x.x%)
	4	n (x.x%)	n (x.x%)
Swelling	Any	n (x.x%)	n (x.x%)
	1	n (x.x%)	n (x.x%)
	2	n (x.x%)	n (x.x%)
	3	n (x.x%)	n (x.x%)
	4	n (x.x%)	n (x.x%)
Swelling (mm)	Any	n (x.x%)	n (x.x%)

Local Reactions and Systemic Events	Grade [1]	GEN-003 60 ug/ M2 50 ug N=xx	Placebo N=xx
	1	n (x.x%)	n (x.x%)
	2	n (x.x%)	n (x.x%)
	3	n (x.x%)	n (x.x%)
	4	n (x.x%)	n (x.x%)
	Any	n (x.x%)	n (x.x%)
	1	n (x.x%)	n (x.x%)
	2	n (x.x%)	n (x.x%)
	3	n (x.x%)	n (x.x%)
	4	n (x.x%)	n (x.x%)
Redness (mm)			
Any Systemic Event	ETC	n (x.x%)	n (x.x%)
Fever	ETC	n (x.x%)	n (x.x%)
Headache	ETC	n (x.x%)	n (x.x%)
Chills	ETC	n (x.x%)	n (x.x%)
Fatigue	ETC	n (x.x%)	n (x.x%)
Nausea	ETC	n (x.x%)	n (x.x%)
Diarrhea	ETC	n (x.x%)	n (x.x%)
Vomiting	ETC	n (x.x%)	n (x.x%)
Muscle aches	ETC	n (x.x%)	n (x.x%)
Any Local Reaction or Systemic Event		n (x.x%)	n (x.x%)
Any Local Reaction		n (x.x%)	n (x.x%)
Pain		n (x.x%)	n (x.x%)
ETC			

Program:

Date Produced: mm/dd/yy

Programming Notes:

- Information comes from the Diary Card
- If a subject has multiple of the same events, take the maximum severity.
- During the 7 day period after the (Days 1-7) a subject should only be counted one time. If a subject has a sign/symptom at least once during that 7 day interval the subject is counted for that sign/symptom.
- Watch page breaks. Please try and keep all the grades together for a sign/symptom.
- Do not include Grade=0 as Grades of 0 imply "None" or no event.
- Fever is based on Temperature (F) which is collected on the Diary Card. See Appendix 2 in the protocol for grade definitions. Grade 1 = 100.4-101.1; Grade 2 = 101.2-102.0; Grade 3 = 102.1-104; Grade 4 >104.

- For Redness (mm) and Swelling (mm), see also Appendix 2 in the protocol. For both redness and swelling: Grade 1 = 2.5-5 cm; Grade 2 = 5.1-10 cm; Grade 3 = >10cm; Grade 4 is Necrosis or exfoliative dermatitis, which we won't be able to determine and will be handled separately as an AE.

[Sponsor]

Protocol: [Protocol number]

page x of y

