From Month 2 to Month 12, the investigational site will contact each subject by telephone or site visit for review of daily electronic reporting tool data and assessment of SAEs, AESIs, and antiviral medication (through Month 6).

A Data Monitoring Committee (DMC) will review safety data at intervals of a minimum of 3 months until all subjects have completed the GEN-003/placebo dosing period. Any additional meetings and the specific safety monitoring plan will be detailed in the DMC charter.

Efficacy Endpoints:

Primary:

- Genital herpes lesion rate (proportion of days with lesions present) in the 6-month period after the maintenance dose: Based on subject report of genital lesions via a daily electronic reporting tool

Secondary:

- Frequency of genital herpes recurrences in the 6-month period after the maintenance dose: Based on subject report of genital lesions via a daily electronic reporting tool
- Proportion of subjects genital herpes recurrence-free at 6 months after the maintenance dose: Based on subject report of genital lesions via a daily electronic reporting tool
- Time to first genital herpes recurrence in the 6-month period after the maintenance dose: Based on subject report of genital lesions via a daily electronic reporting tool
- Duration of genital herpes recurrences in the 6-month period after the maintenance dose: Based on subject report of genital lesions via a daily electronic reporting tool

Safety Endpoints:

- Reactogenicity
 - Local reactions: Pain, tenderness, swelling, redness
 - Systemic events: Fever, headache, chills, fatigue, nausea, vomiting, diarrhea, muscle aches
- AE, SAEs, AESIs, MAAEs

Number of Subjects Planned: Up to 90 subjects

Diagnosis and Main Criteria for Inclusion: Subjects who completed Study GEN-003-003 (completed all study visits including the Month 12 visit) and received all 3 doses of active GEN-003 (any dose combination), received the last dose of GEN-003 within 11 to 18 months, and reported data in daily electronic reporting period on at least 80% of days, and had no important protocol deviation.

Duration of Treatment: 1 dose

Test Product; Dose; and Mode of Administration: GEN-003 (60 µg of each antigen, GB208)

and GB217, 50 µg of MM2, and normal saline), administered as a 0.5 mL IM injection

Control Product; Dose; and Mode of Administration: Normal saline, administered as a 0.5 mL IM injection

Statistical Methods:

Sample Size: No formal sample size calculations were performed for this study.

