10.9.2 Adverse Events

AEs (including SAEs, AESIs, and MAAEs) will be coded using MedDRA and summarized by treatment group for frequency and severity. No formal statistical testing will be performed.

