#### **3.3 Safety Objective**

- To evaluate the safety and tolerability of a maintenance dose of GEN-003 versus placebo

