### **5.3 Randomization**

Eligible subjects were randomized in a 1:1 ratio to receive 1 IM dose of GEN-003 (60 µg each antigen and 50 µg MM2) or placebo. Randomization was stratified on the basis of the GEN-003 dose received by the subject in Study GEN-003-003.

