### **12.2 Adverse Events**

All AEs will be coded using the MedDRA coding system. Frequency tables will be presented by treatment group for all AEs by SOC and PT. Frequency tables will be produced for AEs leading to discontinuation of dosing, by severity, by causality, for most common ( $\geq 5\%$  in any group) AEs, SAEs, MAAEs, and AESIs. Subject listings of all AEs by study day will also be provided.

In all displays, AEs will be displayed by MedDRA SOC and PT, with subjects who have the same AE counted only once for that event and with subjects who have more than 1 AE within a SOC counted only once in that SOC.

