Table No.	Table Title	Analysis Population	IA
14.3.1.4	Frequency Table of All Adverse Events Leading to Discontinuation of Dosing by SOC, Preferred Term and Treatment	Safety	
14.3.1.5	Frequency Table of Subjects with Adverse Events of Special Interest by SOC, Preferred Term, and Treatment	Safety	
14.3.1.6	Frequency Table of All Adverse Events with $\geq 5\%$ Occurrence by SOC, Preferred Term, and Treatment	Safety	
14.3.1.7	Summary of Local Reactions and Systemic Events Occurring Within 7 Days Postdose by Treatment and Maximum Severity	Safety	
14.3.1.8	Descriptive Summary of Duration (days) of Systemic Events and Local Reactions by Treatment	Safety	
14.3.1.9	Summary of Antipyretic/Analgesic Medications Taken Within 7 Days after Maintenance Dose by Treatment Group, Drug Class, and Preferred Term	Safety	
14.3.2.1	Frequency Table of Subjects with Serious Adverse Events by SOC, Preferred Term, and Treatment	Safety	
14.3.2.2	Frequency Table of Subjects with Medically Attended Adverse Events by SOC, Preferred Term, and Treatment	Safety	

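### The programming note for the common adverse event table (SAP Table 14.3.1.6) selects rows on the active arm only, which contradicts the any-group rule in SAP 12.2

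*SAP*

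**What the plan says.** SAP 12.2 lists the AE frequency tables to be produced. One is for the most common AEs, with a 5% threshold that applies "in any group) AEs, SAEs, MAAEs, and AESIs". The table has two columns, GEN-003 and placebo, so any group includes placebo.

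The output that implements this is Table 14.3.1.6. Its programming note reads "Include all SOC/PT where the active treatment group has a ≥ 5% occurrence rate for that SOC/PT". The placebo rate plays no part in that rule.

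The title does not settle the matter. After the 5% figure it continues "Occurrence by SOC, Preferred Term, and Treatment" and names no arm.

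Three other statements set the context:

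- The safety objective is comparative: "To evaluate the safety and tolerability of a maintenance dose of GEN-003 versus placebo" (SAP 3.3).
- SAP 12.2 also requires a table with no threshold: "Frequency tables will be presented by treatment group for all AEs by SOC and PT".
- Protocol 10.9.2 says of AEs: "No formal statistical testing will be performed".

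**The concern.** Both rules are current text, and they cannot both be followed. A programmer working from the shell and a validator working from section 12.2 would produce different tables.

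The difference also has a direction. If a row enters a two-arm table only when one arm reaches a threshold, the table is not neutral between the arms. A term frequent on placebo and rare on active is left out, while the reverse pattern is shown. With a comparative safety objective, a common-AE table should treat the two columns alike. At stake is the balance of one summary display that may be read on its own, without the full AE table beside it.

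**Working it through.** The documents give no figure to reproduce on this point, so the check is a comparison of the two rules followed by an illustration.

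**Rules side by side**

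| Rate on active | Rate on placebo | SAP 12.2 | Note to Table 14.3.1.6 |
|---|---|---|---|
| 5% or more | 5% or more | shown | shown |
| 5% or more | below 5% | shown | shown |
| below 5% | 5% or more | shown | **omitted** |
| below 5% | below 5% | omitted | omitted |

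The rules differ in the third row only. A term commoner on placebo that also reaches 5% on active stays in under both.

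**Arm size.** The protocol synopsis gives "Number of Subjects Planned: Up to 90 subjects" and SAP 5.3 states that "Eligible subjects were randomized in a 1:1 ratio to receive 1 IM dose of GEN-003" or placebo. That is at most about 90 / 2 = 45 per arm. The actual number is not stated, so a range is needed.

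**The cut in subjects** is the smallest whole number k with k/n at or above 0.05:

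- n = 21 to 40: 0.05 × 21 = 1.05 and 0.05 × 40 = 2.00, so k = 2.
- n = 41 to 60: 0.05 × 41 = 2.05 and 0.05 × 60 = 3.00, so k = 3.

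**Example at 45 per arm (k = 3).** A term in 2 active subjects (2/45 = 4.4%) and 6 placebo subjects (6/45 = 13.3%) is omitted under the note and shown under 12.2. With the counts reversed it is shown under both. The example depends on arm size: at 40 per arm, 2/40 = 5.0% meets the cut and the same counts would be shown.

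**Chance that 12.2 keeps a term and the note drops it**, at 45 per arm with independent arms and assumed true rates: P(active count ≤ 2) × P(placebo count ≥ 3), both exact binomial.

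| True rate, active / placebo | Calculation | Result |
|---|---|---|
| 2% / 10% | 0.939 × 0.841 | 0.79 |
| 4% / 10% | 0.732 × 0.841 | 0.62 |
| 5% / 5% | 0.608 × 0.392 | 0.24 |
| 10% / 20% | 0.159 × 0.997 | 0.16 |

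**Direction of the tilt.** Take a term with a true rate of 5% in both arms, at 45 per arm. Given that the note keeps it, the expected active rate is 0.05 × P(Bin(44, 0.05) ≥ 2) / P(Bin(45, 0.05) ≥ 3) = 0.05 × 0.653 / 0.392 = 8.3%. The placebo rate is unaffected by the selection, at 5.0%. Under the either-group rule both arms have the same expected rate, 6.3%. With 30 and 40 per arm the note gives 8.7% and 7.2% on active, against 5.0% on placebo.

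**The case against.** The strongest reply is that very little is lost. Every AE appears by arm, with no threshold, in Table 14.3.1.1, again by severity in 14.3.1.2 and by causality in 14.3.1.3, and in Listing 16.2.7.3. SAEs, AESIs and MAAEs have their own unfiltered tables. Solicited reactions, which carry much of the tolerability information for a vaccine, go on the Diary Card and stay off the AE form unless they meet SAE criteria (Protocol 6.1). They are reported in Tables 14.3.1.7 and 14.3.1.8, which have no 5% filter. All of this stands, and it limits the point to one display.

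It can also be said that nothing in the documents gives the shell precedence over section 12.2, and that SAP 5.6 provides for validation, which might catch the mismatch. That is fair, but validation would then have to choose between two written rules.

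A reader might infer more than the documents support:

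- *That events commoner on placebo vanish from the comparison.* They do not. Only those below 5% on active and at or above 5% on placebo are omitted, and only from this table.
- *That the note conceals vaccine risk.* It cannot hide any event that reaches 5% on active. The tilt runs against the product.

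**Conclusion.** The inconsistency is real and the note is wrong as written against SAP 12.2. Its effect is small: a one-sided selection of rows in Table 14.3.1.6, with no data lost and no test or estimate changed. The contradiction itself rests on no assumption. The size of the effect does: arm size, true AE rates and independence between arms are assumed for illustration. The asymmetry is present at every arm size considered, although which individual terms fall out changes between 40 and 41 per arm. This is a minor correction, worth making because it alters an output and costs almost nothing.

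**What to change.** In the programming note to Table 14.3.1.6, replace the reference to the active treatment group with either treatment group, so that it matches section 12.2. Add a footnote to the table stating that rows are included when the rate is 5% or more in either arm.

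If selection on the active arm was intended, section 12.2 would have to change instead and the table would have to declare its one-sided rule. The either-group rule suits the comparative objective better.

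The cost is one edited line and one footnote. No new data or additional analysis is needed.

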**Table 14.3.1.8: Descriptive Summary of Duration (days) of Systemic Events and Local Reactions by Treatment**

Safety Population

Systemic Events and Local Reactions	Statistic	GEN-003 60 ug/ M2 50 ug N=xx	Placebo N=xx
Fever	N	xx	xx
	Median	xx.x	xx.x
	Minimum	xx	xx
	Maximum	xx	xx
Headache	N	xx	xx
	Median	xx.x	xx.x
	Minimum	xx	xx
	Maximum	xx	xx
Chills	N	xx	xx
	Median	xx.x	xx.x
	Minimum	xx	xx
	Maximum	xx	xx
Fatigue	N	xx	xx
	Median	xx.x	xx.x
	Minimum	xx	xx
	Maximum	xx	xx
Nausea	N	xx	xx
	Median	xx.x	xx.x
	Minimum	xx	xx
	Maximum	xx	xx
Dairrhea	N		
	Median		
ETC...	ETC...		

Program:

Date Produced: mm/dd/yy

Programming Notes:

- Information comes from the Diary Card
- For start date, use the date from when the symptom is first recorded on the card (severity >0). For the stop date, use the date when the symptom is last present on the card (severity > 0). If a stop date is not available, then this needs to be given to the CDM.

[Sponsor]

Protocol: [Protocol number]

page x of y

**Table 14.3.1.9: Summary of Antipyretic/Analgesic Medications Taken Within 7 Days after Maintenance Dose by Treatment Group, Drug Class and Preferred Term**

Safety Population

Preferred Term	GEN-003 60 ug/ M2 50 ug N=xx	Placebo N=xx
Any Anti-Fever/Anti-Pain Medication	n (x.x%)	n (x.x%)
Preferred Term 1	n (x.x%)	n (x.x%)
Preferred Term 2	n (x.x%)	n (x.x%)
Preferred Term 3	n (x.x%)	n (x.x%)
etc.		

Program:

Date Produced: mm/dd/yy

Programming Note:

- Antipyretic/analgesic medications are defined as medications with an ATC2 Class of 'ANALGESICS' or 'ANTIINFLAMMATORY AND ANTIRHEUMATIC PRODUCTS'

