3 STUDY DESIGN

3.1 Overall Study Design

This study is a randomized, double-blind, placebo-controlled clinical trial of GEN- 003 in subjects who have received previous doses of GEN-003. Subjects who completed Study GEN-003-003 and received all 3 doses of GEN- 003, reported data in daily electronic reporting period on at least 80% of days, and had no important protocol deviation in that trial will be offered enrollment in this study. Subjects who meet all inclusion and no exclusion criteria and provide written informed consent for this study will be randomized within 11 to 18 months after the last active GEN-003 dose in a 1:1 ratio to receive 1 IM dose (the maintenance dose) of GEN-003 or placebo. Randomization will be stratified on the basis of the GEN-003 dose received by the subject in Study GEN-003-003.

Subjects will use a daily electronic tool for reporting the presence or absence of genital herpes lesions and the severity of genital herpes symptoms from Day 1 until the Month 6 Visit.

Subjects will complete the EuroQol – 5 Domains – 5 Levels (EQ-5D-5L) questionnaire on each day of the first recurrence after the maintenance dose through Month 6.

A serum sample will be collected from each subject for future research purposes before the maintenance dose (Day 1), 7 and 28 days after the maintenance dose (Day 8 and Day 29/Month 1).

At selected investigational sites, a whole blood sample will be collected and processed to isolate peripheral blood mononuclear cells (PBMCs) for future research purposes before the maintenance dose (Day 1), 7 and 28 days after the maintenance dose (Day 8 and Day 29/Month 1).

Local reactions and systemic events will be recorded for the first 7 days after the maintenance dose on the paper Diary Card; if any event is ongoing after Day 8, it will be followed until resolution. All AEs and concomitant medications will be recorded from Day 1 to Day 29/Month 1. After Day 29/Month 1 to the end of the study, only SAEs, AESIs, MAAEs, antiviral medications, and vaccines will be recorded. All AEs will be graded in accordance with the Toxicity Grading Scale for Healthy Adult and Adolescent Volunteers Enrolled in Preventive Vaccine Clinical Trials from Grade 1 (mild) to Grade 4 (life-threatening) ([Appendix 2](#)).

From Month 2 to Month 12, the investigational site will contact each subject by telephone or site visit for review of daily electronic reporting tool data and assessment of SAEs, AESIs, and antiviral use (through Month 6).

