Diary Card – Subjects will be provided a Diary Card to record local reactions, systemic events, and oral temperature for the 7 days after the maintenance dose. If there are any events ongoing after Day 8, these events will be followed until resolution and the stop date recorded. The Investigator (or Subinvestigator) will review Diary Cards with the subject. Any changes or comments to the subject's Diary Card must be made on the Diary Card and initialed and dated by the Investigator (or Subinvestigator). The Diary Card **AND** the Investigator's (or Subinvestigator's) assessment will serve as the source document. A sample of the Diary Card is provided in [Appendix 3](#).

An event recorded on the Diary Card should not be recorded on the AE eCRF unless it meets the criteria of an SAE.

AEs (including SAEs, AESIs, and MAAEs) – refer to [Section 7](#).

AEIS – refer to [Appendix 4](#) for list.

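### Read literally, SAP Table 14.3.1.8 ends each solicited reaction at its last Diary Card day and does not use the resolution date that the protocol records

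*SAP*

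**What the plan says.** SAP 12.1 summarises the duration of local reactions and systemic events in days, by count, median, minimum and maximum. The programming notes to Table 14.3.1.8 give the source, "Information comes from the Diary Card", and the end-date rule, "For the stop date, use the date when the symptom is last present on the card (severity > 0". The start is the first day the symptom is recorded with a severity above zero. The note closes with: "If a stop date is not available, then this needs to be given to the CDM".

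The sample card in Protocol Appendix 3 has eight daily rows, Days 1 to 8. Protocol 6.1 says: "If there are any events ongoing after Day 8, these events will be followed until resolution and the stop date recorded". Protocol 6.2.1 gives the subject the matching instruction to report that date. Protocol 6.1 also keeps these reactions off the adverse event form in most cases: "An event recorded on the Diary Card should not be recorded on the AE eCRF unless it meets the criteria of an SAE".

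**The concern.** The protocol collects the true end of a long reaction, and the only SAP table on reaction duration is not told to use it. A programmer who follows the note would close every reaction that is still present on the last card row at that row. The longest reactions would then be shortened to the length of the form.

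Safety and tolerability of the maintenance dose is a stated objective, and reactogenicity is a listed safety endpoint. The maximum duration is where a reader looks for prolonged reactions. Non-serious diary reactions do not go onto the adverse event form, so the adverse event tables and listings, which carry stop dates, would not supply the missing information. The mock-ups of the two diary listings (16.2.7.1 and 16.2.7.2) show no stop-date column.

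**Working it through.** The plan states no figure for this point, so there is none to reproduce. The check is day arithmetic.

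**Inputs**
- Last row of the sample card: Day 8 (Protocol Appendix 3).
- End-date rule: last symptomatic card day (SAP Table 14.3.1.8 notes).
- True stop date: recorded for reactions ongoing after Day 8 (Protocol 6.1 and 6.2.1).
- Statistics reported: count, median, minimum, maximum (SAP 12.1).

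**Step 1: the cap.** Counting both end days:
- true duration = stop − onset + 1
- duration under the literal rule = min(stop, 8) − onset + 1

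| Onset | True stop | True duration (days) | Literal rule (days) |
|---|---|---|---|
| Day 1 | Day 8 | 8 | 8 |
| Day 1 | Day 10 | 10 | 8 |
| Day 1 | Day 14 | 14 | 8 |
| Day 1 | Day 21 | 21 | 8 |
| Day 2 | Day 14 | 13 | 7 |
| Day 3 | Day 14 | 12 | 6 |

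The stop days after Day 8 are illustrative. The cap itself follows from the card and the rule.

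**Step 2: which statistic moves.** Assume 40 subjects with a given reaction, all starting on Day 1. Reactions that resolve on the card last 3 days; those that outlast it truly last 12 days and are reported as min(12, 8) = 8. These values are assumptions chosen to show the pattern. With 40 values, the median is the mean of the 20th and 21st.

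| Share outlasting the card | Median, true / literal rule | Maximum, true / literal rule |
|---|---|---|
| 0% | 3 / 3 | 3 / 3 |
| 5% (2 of 40) | 3 / 3 | 12 / 8 |
| 40% (16 of 40) | 3 / 3 | 12 / 8 |
| 50% (20 of 40) | (3 + 12)/2 = 7.5 / (3 + 8)/2 = 5.5 | 12 / 8 |
| 60% (24 of 40) | 12 / 8 | 12 / 8 |

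In this example two long reactions are enough to make the maximum wrong. The median is unaffected until about half of the reactions outlast the card.

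**Step 3: the rule can also lengthen.** It runs from first to last symptomatic day. A symptom present on Days 1, 2 and 6 has 3 symptomatic days but is reported as 6 − 1 + 1 = 6. The rule therefore does not shorten every duration.

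**Step 4: does the CDM sentence close the gap?** It applies when a stop date is not available. A symptom present on the last card row already has a last-present date under the sentence before it, so on a literal reading the referral is not triggered. If it is triggered, the note does not say which date comes back or how it enters the table.

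**The case against.** The best defence is that the note is incomplete, not wrong. The CDM sentence may have been written for reactions with no end on the card. Listings 16.2.7.1 and 16.2.7.2 allow for days beyond the first seven being captured. Protocol 6.1 has changes and comments written on the card itself, so a late stop date might reach the database that way. The eight rows come from a sample card. All this stands as a reason to call truncation a risk from an unclear rule and not a certainty. It does not settle the matter: the listing notes govern what is displayed, and no text names the recorded resolution date as the stop date for the duration table.

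Three stronger readings are tempting, and the documents do not support them.

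- **Reactogenicity is understated in general, and the difference between arms is narrowed.** Shortened reactions stay in the count and in the incidence table; only their length is exposed. In the parent trial, Grade 3 reactions occurred in 51.2% (60/50 group) against 13.6% (placebo), and swelling in 64.4% of active subjects. These are incidences after any dose of a three-dose series, and the swelling figure pools both active groups. They say nothing about how long reactions last after one dose.
- **Table 14.3.1.7 wrongly leaves out Day 8.** Its note reads "During the 7 day period after the (Days 1-7) a subject should only be counted one time", and Protocol 3.1 places a visit "7 and 28 days after the maintenance dose (Day 8 and Day 29/Month 1". That protocol text is about blood sampling. A first week of seven daily entries can fairly mean Days 1 to 7, as the diary listings show it. The card is filled in each evening and brought to a visit at Day 8 ± 3, so the Day 8 row may be blank for subjects seen on or before that day. Counting it would make observation depend on visit timing.
- **A reaction that first appears on Day 8 is lost altogether.** Table 14.3.1.8 has no Days 1 to 7 limit, so a Day 8 onset recorded on the card would still enter that table, and the listings show additional days with symptoms.

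**Conclusion.** The stop-date point holds. Followed literally, the note to Table 14.3.1.8 caps duration at the card's end although the true end date is collected. On the sample card the cap is 8 days for a Day 1 onset, 7 for Day 2 and 6 for Day 3.

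The reported maximum is understated whenever the longest reaction runs past the card. The median is understated only if about half or more of the reactions do so. How many reactions are affected, and whether the arms differ in this, cannot be derived from the documents.

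The conclusion assumes that the study card matches the sample and that the programmer takes the note as written. The table is descriptive; incidence, maximum severity and all efficacy analyses are unaffected. It is a modest correction to a safety table, worth making before the table is programmed.

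**What to change.** Replace the stop-date part of the Table 14.3.1.8 programming note with three rules:

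1. If the reaction is ongoing after the last card day, the stop date is the recorded resolution date.
2. Otherwise, the stop date is the last card day with a severity above zero.
3. If the reaction outlasts the card and its stop date is unknown or it is unresolved, flag it as ongoing (censored), do not end it at the last card day, and show the number of such reactions by arm. This also fits SAP 5.5.1, which rules out imputation.

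Leave the Days 1 to 7 count in Table 14.3.1.7 as it is. At most, add a sentence that reconciles the eight-row card with that window.

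The cost is one programming note and a footnote to the table. The protocol already has the resolution dates recorded, so no new data are needed.
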